PROTOCOL: Racial Differences in the Natriuretic Peptide Response to Glucose Challenge

Study Design, Setting, and Location

Our study was a single-center, prospective, physiological clinical trial approved by the institutional review board at the University of Alabama at Birmingham (UAB). Participants were recruited from the university campus and surrounding areas. All participants signed informed consent.

Sample Selection

Prospective participants were first contacted by phone to determine eligibility prior to scheduling a screening visit at the clinical research unit (CRU). Self-identified healthy black and white men and women were eligible to participate in the clinical trial based on the following criteria: between 18 and 40 years of age, blood pressure (BP) less than 140/90, estimated glomerular filtration rate >60 ml/min, and willingness to adhere to the study diet. Exclusion criteria included the following: history of hypertension, history of cardiovascular, renal, or liver disease, history of diabetes or glucose-lowering medications, use of vasoactive or diuretic medications, anemia, abnormal serum sodium or potassium, pregnancy, elevated liver function tests defined as >3x the upper limit of normal, women taking hormonal birth control, history of smoking, body mass index (BMI) <18.5 kg/m², or regular use of non-steroidal anti-inflammatory medications.

Study Protocol

For the screening visit, subjects were educated on the study protocol and directed to complete a questionnaire regarding medical and family history. The study investigators further evaluated subjects who agreed to the study and signed consent. Blood was drawn for a basic metabolic profile, liver enzymes, and complete blood count. Additional samples were collected if consent was provided for DNA extraction and gene expressions for NPs. The CRU nursing staff obtained height, weight, and BP (i.e., an average of three BP measurements) for a baseline. Female participants provided a urine sample to test for pregnancy. Before completion of the screening visit, subjects met with the registered dietitian to discuss the study diet and were provided with a 3-day meal log to assess dietary habits.

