Upon review of screening labs, eligible subjects were enrolled in the study [stratified by race using permuted blocks for age and sex] and invited back for food pick up and protocol (i.e., a high-carbohydrate challenge) visits. Within seven days after the screening visit, participants visited the CRU metabolic kitchen for food pick-up. Three days of standardized meals were provided to be consumed for the three days leading up to the protocol visit. Three meals per day and snacks were provided based on participant preferences and by following macronutrient RDAs from the USDA 2005 Guidelines. The study nutritionist calculated caloric needs. In brief, each study participant was provided on an average 1,993 kilocalories worth of meals comprising 4,667 mg of sodium per day for three days. The contribution of carbohydrate, fat, and protein in total caloric intake was 51%, 31%, and 18%, respectively. Additional instructions were given to drink only water, to refrain from alcohol and caffeine use, and to consume only

food provided by CRU metabolic kitchen for the remainder of the study. Participants were also advised to avoid strenuous activities for 24 hours prior to the protocol visit. For the protocol visit, participants fasted overnight for 10 hours, before reporting at 7:00 AM to the CRU. Upon arrival, participants were assessed for compliance with the study diet and were positioned in the sitting position with the back-rest at 45 degrees and legs elevated. Heart rate, oxygen saturation and BP (an average of three measurements using a Carescape V100 monitor) were obtained. Participants were given glucola, a 75mL, 75g glucose equivalent, and were provided only distilled water to drink as needed for the remainder of the protocol. Blood pressure was measured every 30 minutes, and heart rate and oxygen saturation were measured every 60 min. Blood was drawn in 60 min intervals for 8 hours for biomarker profiling. All the participants remained in fasting state (except distilled water) till the end of the study protocol.

Statistical Analyses

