All analyses were conducted using STATA, version 14.2 MP (StataCorp LP), and LIMMA R package. Baseline characteristics of participants were compared between blacks and whites using Student's t-test (normal distribution) or Mann-Whitney test (non-normal distribution) for continuous variables and Pearson χ^2 test for categorical variables. The normality of continuous variables was assessed using histogram and Q-Q plots (visual assessment) as well as Shapiro Wilk test (statistical assessment). Plasma NP levels at baseline and after a high-carbohydrate challenge were found to have a non-normal distribution and were log-transformed for the analyses. Linear regression models were used to assess the racial differences in plasma NP levels. Choosing white race as a reference, a relative percentage difference in plasma NP levels with 95% confidence interval (CI) in blacks was calculated using the following formula: $(e^{\beta} - 1) \times 100$ (where β is the beta coefficient from linear regression). Linear mixed-effect models excluding missing data (<1%) from 72 individuals were used to assess the effect of a high-carbohydrate challenge over time on plasma NP levels. In these models, we assessed for repeated measurements of NP levels with fixed effects of race, time, and their multiplicative interaction term (race*time), accounting for the correlation among repeated measures in the same person. Participants were treated as random effects in these models. The percentage difference with 95% CI in plasma NP levels after 8 hours in overall as well as by race was calculated: $[(e^{\beta} - 1) \times 100 \text{ multiplied by 8 hours (where } \beta \text{ is the beta coefficient from linear regression)}]$. The models mentioned above were further assessed after adjusting for their baseline demographics [i.e., age, sex, body mass index (BMI), insulin].

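### Adjusting for baseline age, sex, BMI and insulin as main effects leaves the racial difference in natriuretic peptide response essentially unadjusted

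*Combined protocol and SAP*

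**What the plan says.** All of this is in the combined protocol and SAP.

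- The title sets the question: "Racial Differences in the Natriuretic Peptide Response to Glucose Challenge".
- Statistical Analyses gives the mixed model "fixed effects of race, time, and their multiplicative interaction term (race*time"), and adds "Participants were treated as random effects in these models".
- The reported response is the 8-hour change: "The percentage difference with 95% CI in plasma NP levels after 8 hours in overall as well as by race was calculated".
- The adjustment is one sentence: "The models mentioned above were further assessed after adjusting for their baseline demographics [i.e., age, sex, body mass index (BMI), insulin". It covers both the linear regressions of peptide level on race and the mixed models. It does not say whether the covariates enter alone or also in interaction with time.
- On the data: "Blood was drawn in 60 min intervals for 8 hours for biomarker profiling" (Study Protocol), and "Linear mixed-effect models excluding missing data (<1%) from 72 individuals" (Statistical Analyses).
- On balance between the races, the Study Protocol says enrolment was "stratified by race using permuted blocks for age and sex". Nothing comparable is stated for BMI or insulin.

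**The concern.** Race is not randomised, so a difference between the races in how peptides respond could reflect another characteristic that differs by race and also changes the response. Blocking on age and sex at enrolment limits that risk for those two. BMI and insulin are left to the model.

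The covariates are baseline values, fixed within each participant. Entered as main effects they can explain why one person's curve lies higher than another's, but not why it falls faster. If BMI or insulin both differed by race and modified the response, race×time would carry that effect in the adjusted model exactly as in the unadjusted one. A reader who saw the two response results agree would take it as evidence that BMI and insulin do not explain the difference. It would be no such evidence, because the model could hardly have given any other answer.

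**Working it through.** **The plan's own figure, for scale.** Inputs from Statistical Analyses: SD 0.2, n = 30, power 0.8, α = 0.05 (taken as two-sided).

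- Normal formula: 0.2 × (1.960 + 0.842) / √30 = 0.102, which is 10.8% as an increase or 9.7% as a decrease.
- Noncentral-t version: 0.106, which is 11.2% or 10.0%.

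The stated 11% reproduces. It is a change within one group, not a racial difference.

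**Algebra.** Write log peptide for person i at hour t as

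y = a + r·race + d·t + g·race·t + c·X + person effect + error,

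with X the baseline covariates. Person i's fitted slope is Σ(t − t̄)y / Σ(t − t̄)². The term c·X is the same at every t, so it enters as c·X × Σ(t − t̄) = 0. With common, complete time points, g is the difference between the mean slopes of the two races, with or without X. The estimate of d is likewise unaffected.

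**Simulation A** (assumed design: 30 + (72 − 30 = 42) participants; 9 samples at hours 0 to 8, so 72 × 9 = 648 values; random-intercept model fitted by REML; average slope ln(0.73)/8 = −0.0393 per hour, from the plan's 27%; residual SD 0.2; between-person slope SD 0.01; BMI SD 4.5; no true race effect on slope).

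- Complete data, 50 data sets: main effects changed time and race×time by at most 2.2e-16.
- 6 of 648 values deleted (0.9%), 60 data sets in each of six scenarios: race×time moved by at most 0.0074 SE.
- In one complete data set the race main effect did move, from −0.223 to −0.255.

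**Simulation B** (independent; 36 + 36 participants; generalised least squares with known variances; 200 data sets per setting; BMI gap 2 kg/m² with slope effect −0.003; insulin gap 0.5 SD with slope effect −0.008 per SD; true race×time zero). The slope difference built in through the covariates is 2 × (−0.003) + 0.5 × (−0.008) = −0.010 per hour.

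| Complete data, random intercept | Unadjusted | Main effects | Covariate×time |
|---|---|---|---|
| Mean race×time per hour | −0.0094 | −0.0094 | +0.0002 |
| SE | 0.0061 | 0.0061 | 0.0066 |
| Over 8 hours, (exp(8g) − 1) × 100 | −7.3% | −7.3% | +0.2% |

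The SE checks by hand: Σ(t − t̄)² = 60 for hours 0 to 8, and √[(0.2²/60) × (2/36)] = 0.0061. The largest change from main effects was below 1e-16 with complete data, with or without a random slope. With 6 values missing it was 0.009 SE (random intercept) or 0.014 SE (random slope). The race coefficient at time 0 moved from −0.39 to −0.26, so levels are adjusted and slopes are not.

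**Possible size.** What main-effect adjustment leaves in race×time is gap × effect on slope. The documents give neither, so these are assumed ranges: a BMI gap of 0 to 3 kg/m² and an effect of 0 to 0.004 log units per kg/m² per hour.

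- Lower end: 0 per hour, 0% over 8 hours.
- Upper end: 3 × 0.004 = 0.012 per hour; exp(8 × 0.012) − 1 = 10.1%.
- At 3 kg/m² and 0.002 the expected value is 0.006 per hour, or exp(0.048) − 1 = 4.9%. Simulation A gave means of 0.0067 unadjusted, 0.0067 with main effects, and 0.0007 with age, sex and BMI×time.

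**The case against.** **The text does not fix the reading.** Covariate×time terms may have been fitted and not written down. That stands, and the conclusion is conditional on it. But the plan spells out race×time and no other interaction, so main effects is what an analyst following it would fit. If interactions were fitted, the plan still needs to say so.

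**The race contrast may not be the main target.** The study is powered on a change within Black participants, and the stated 8-hour results are changes overall and within each race. A covariate imbalance between races does not bias a descriptive within-race change. That also stands. The point concerns race×time, which is in the model and is what the title asks about. Nor does the plan claim that its adjustment rules out BMI or insulin; the risk lies in how an unchanged result would be read.

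**Confounding is assumed, and the top of the range is generous.** At 0.004 and a BMI SD of 4.5, one SD of BMI would change the 8-hour response by 4.5 × 0.004 × 8 = 0.144 log units, about 46% of the assumed mean response of 0.315 (−ln 0.73). The 11% is not a like-for-like benchmark either. With SD 0.2 and 30 + 42 participants, the detectable racial difference is 0.2 × 2.802 × √(1/30 + 1/42) = 0.134 log units, or 14%. Both points are fair. The range therefore starts at zero and is illustrative, but the structural result does not depend on it.

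**BMI and insulin may lie on the path from race to response.** Whether to remove them is a choice of estimand. The plan has already chosen to adjust for them; this is a reason to report results with and without them, and to keep insulin in a model of its own.

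**Conclusion.** The concern holds. On the natural reading, the adjusted response analysis is in effect the unadjusted one: identical with complete data, and within 0.014 SE in simulations with about 1% of values missing. This follows from fixed baseline covariates, a common sampling schedule and near-complete data, and needs no assumed effect size. Baseline insulin is taken at its word; insulin measured over time would behave differently.

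The size of any resulting bias is unknown. It is zero unless BMI or insulin both differs by race and modifies the response, and it reaches 10.1% over 8 hours at the upper corner of the assumed BMI range. The adjusted comparisons of peptide levels are not affected. This is a worthwhile and inexpensive correction; it does not invalidate the unadjusted analysis.

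**What to change.** 1. State how the covariates enter each adjusted model.
2. If an adjusted racial difference in response is reported, add centred age×time, sex×time and BMI×time to the adjusted mixed model and read the difference from race×time there. Fit baseline insulin×time in a separate further model.
3. Alternatively, regress each participant's fitted slope on race plus the covariates. With complete data this gave the same coefficient (difference at most 2e-16). Do not substitute the two-point 8-hour change score: it is a different estimator, differing by 0.005 per hour on average in absolute value, with an SE 1.39 times as large in simulation A.
4. Report the unadjusted race×time alongside, and label the added terms post hoc if they are introduced after the data were seen.

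The cost is SAP wording and three or four terms on data already collected, plus some precision. With age, sex and BMI×time, the SE of race×time rose on average by 1% to 7% as the BMI gap went from 0 to 3 kg/m², and by up to 20% in a single data set. With all four covariate×time terms in simulation B it rose by 9% to 10% (for example 0.00609 to 0.00664). With no BMI gap, the added terms moved race×time by only about 0.3 SE on average.
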